**The I-FiBH Trial: Intravenous Fluids in Benign Headaches Trial: A Randomized Single
Blinded Clinical Trial**

NCT 03185130

March 15, 2017

INTRODUCTION

Migraine headache has a 1-year period prevalence in the US of 11.7% and accounts for approximately 1.2 million migraine visits to US emergency departments per year [1,2]. There are numerous studies that discuss treatment for migraine and other benign headaches within the emergency department, however, there are very few that discuss specifically the use of intravenous fluids (IVF) for headache treatment [3]. Many of these studies look at various options for treating migraine and other benign headaches: treatment options include dopamine antagonists, opioids, non-steroid anti-inflammatory drugs (NSAIDs), triptans, anti-epileptics and ergot derivatives [2]. Comparisons have been done between many of these treatment options with dopamine antagonists appearing to be the most effective, compared to other treatments [4, 5, 6, 7]. The dopamine antagonist with the most evidence and availability for benign headaches is prochlorperazine [6, 7, 8, 9, 10, 11, 12].

Peripheral IVs and administration are common procedures and treatments within the ED. And while relatively safe, they are not without their own risks [13, 14, 15, 16]. Given that IVF administration is a common part of treatment regimen for benign headache patients in the emergency department and given the lack of randomized trials in adults, we aim to study the use of IVF on pain reduction in headache patients in the adult ED [3]. Given the specific definition of migraine headache, we have chosen to categorize our headaches as benign headaches, avoiding the difficulty of determining if a patient meets the specific criteria for migraine headache [17, 18]. There has been one randomized trial in pediatrics that shows IVF may help in patients with migraines, whereas the adult literature has no randomized control trials and a review of data shows that fluids do not help relieve pain in migraine headache patients [3, 19, 20].

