The risks are the side effects associated with each drug. For prochlorperazine, this includes drowsiness, blurred vision, xerostomia, congestion, nausea, akathisia, tardive dyskinesia, NMS, and blood dyscrasias. For Benadryl include sedation, tiredness, sleepiness, dizziness, constipation, dry mouth, blurred vision, nausea, and loss of appetite. For normal saline, this

includes injection site swelling, redness, infection, venous thrombosis or phlebitis or hypervolemia. Personal benefits include intended reduction in headache symptoms and the satisfaction that the patient may be assisting investigators in determining a more effective headache treatment.

Interventions

After enrollment, each patient will be randomized either to the standard treatment arm to receive prochlorperazine 0.15 mg/kg up to 10 mg IV along with diphenhydramine 1mg/kg (up to 50 mg) IV and normal saline at 5 mL/h IV OR to the study arm to receive prochlorperazine along with diphenhydramine IV and normal saline at 20 mL/kg (up to 1000 mL) given IV over 1 hour. The diphenhydramine will be administered first, and immediately afterward the prochlorperazine will be administered. The patient will then be connected to normal saline on an IV pump and randomized to 5 cc over an hour or 20 cc/kg (maximum 1000 cc) over one hour. The IV bag and pump will be covered so that the patient will not know how much fluid they are receiving. Patients will undergo simple randomization to either the fluid bolus group or the control group. The treating physician will consult a folder that contains a list specifying the group assignment. Each row of the list corresponded to a patient, and will be covered by a small slip of opaque paper that will be removed at the time of enrolment to reveal the group assignment. This list was constructed at the beginning of the study using a random number generator by a research staff. Randomization in the pediatric ED and adult ED will be separate to ensure equal numbers of pediatric patients in both the experimental and control arms (blocking). Emergency providers will be instructed not to administer any rescue medications for at least 30 minutes.

Safety

After 30 minutes, the treating provider will be permitted to administer a “rescue medication” of their choice for further treatment. If there is an untoward event that requires the patient to know which IVF dose was administered, patient will unblinded and will not continue in the study.

Reportable Events

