Anticipated side effects are those listed on the manufacturer’s package insert and are treated as routine non-urgent or non-emergent events are not reportable events.

Adverse Events are those unanticipated side effects that require interventions or anticipated side effects that do not respond to intervention.

Serious Adverse Events are those side effects that require Advanced Life Support measures to control symptoms.

AEs and SAEs will be reported to the IRB within 5 days of the event.

Methods of Measurement

Enrolled patients will fill out a brief data collection form to include age, sex, race, phone number, and baseline headache severity using a 100-mm visual analog scale (VAS). Repeat headache severity scores will be measured at 30 and 60 minutes. Time zero begins immediately after complete administration of the study drug. Nausea (with a 100 mm VAS) and vomiting will also be assessed at these time intervals. The need for rescue medications will be extracted from the patient's chart at a later time.

Trained research assistants will call the patient 24-48 hours post-discharge by phone to ask if they are currently having a headache (yes or no) and to rate their current pain (0-10). If the patient is admitted, the patient will be approached in the hospital by an investigator or research assistant for follow up.

Outcome Measures

The primary outcome measure will be the difference in pain scores between the 5 cc over an hour and 20 mg/kg (up to 1000 cc) over an hour groups measured as the absolute difference between the means at 60 min. Secondarily, we will measure the difference between the rates of decline in pain scores, rate of admission, nausea scores, rate of vomiting, rate of use of additional medications for headache, and headache resolution with telephone follow up.

Privacy and Security

In order to protect the privacy of the research subjects and to maintain the confidentiality of data, all data will be managed only by trained research assistants or investigators and will be stored in the locked Emergency Medicine research offices and electronic data will be stored on a password protected computer in the locked Emergency Medicine research office. All research assistants and investigators are HIPAA- trained, CITI trained and credentialed by UMC IRB, and oriented to the study protocol.

Data Analysis:

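### No scheduled contact asks about the saline and IV-site risks the protocol names, so the trial will have no rate by arm for any of them

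*Combined protocol and SAP*

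**What the plan says.** - **Risk/Benefit.** For normal saline the list "includes injection site swelling, redness, infection, venous thrombosis or phlebitis or hypervolemia". Counted singly, that is six risks.
- **Introduction.** On peripheral IVs and their use: "And while relatively safe, they are not without their own risks".
- **Interventions.** Both arms receive IV diphenhydramine, IV prochlorperazine and saline on a pump. Patients are "randomized to 5 cc over an hour or 20 cc/kg (maximum 1000 cc) over one hour". The treating physician uncovers the assignment; the patient is blinded.
- **Methods of Measurement.** In the ED: "Repeat headache severity scores will be measured at 30 and 60 minutes", and "Nausea (with a 100 mm VAS) and vomiting will also be assessed at these time intervals". From the chart: "The need for rescue medications will be extracted from the" patient's record. After discharge there is one call, at 24-48 hours, "to ask if they are currently having a headache (yes or no) and to rate their current pain (0-10"). Admitted patients are seen in hospital, but the content of that contact is not given.
- **Outcome Measures.** Apart from pain scores and their rate of decline, the outcomes are "rate of admission, nausea scores, rate of vomiting, rate of use of additional medications for headache, and headache resolution with telephone follow up".
- **Reportable Events.** Anticipated effects are defined by the package insert and are not reportable when handled as routine. An anticipated effect becomes an adverse event only if it fails to respond to intervention. Adverse and serious adverse events go to the IRB within 5 days.
- **Data Analysis.** No safety analysis is described.

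**The concern.** The randomized exposure is the volume of fluid, and the protocol itself says what harm the fluid can do. It specifies what is asked at 30 minutes, at 60 minutes and on the call, and none of those questions concerns such a harm. The Reportable Events section does not fill the gap. It says what to do with an event once known, not how to find one, and it leaves out routine anticipated effects. A sore, red or swollen site the day after discharge would reach the team only if the patient volunteered it, and even then it would probably not be reportable.

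Information that was never requested cannot be recovered at analysis. A report that no fluid-related events were seen could mean that none occurred or that nobody asked, and a reader could not tell which.

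**Working it through.** **1. Named risks against scheduled questions.**

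| Named saline risk | 30 min | 60 min | 24-48 h call | Outcome |
|---|---|---|---|---|
| Site swelling | no | no | no | no |
| Site redness | no | no | no | no |
| Infection | no | no | no | no |
| Venous thrombosis | no | no | no | no |
| Phlebitis | no | no | no | no |
| Hypervolemia | no | no | no | no |

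Zero of six are asked about at any contact whose content is specified. The in-hospital contact cannot be scored because its content is not stated.

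**2. The plan's sample size.** Inputs from Data Analysis: SD 22 mm, difference 13 mm, alpha 0.05 (taken as two-sided), power 80%.

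n = 2(1.960 + 0.842)² × 22²/13² = 2 × 7.849 × 2.864 = 44.96, so 45 per group.

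The stated figure is reproduced. Using the t distribution, power at 45 is 79.2%. Nothing in this point changes it.

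**3. What a zero count would mean if every patient were asked.** The exact upper limit for 0 of n is 1 − a^(1/n).

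- Two-sided 95%: 1 − 0.025^(1/45) = 0.0787, or 7.9%.
- One-sided 95%: 1 − 0.05^(1/45) = 0.0644, or 6.4%.

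**4. What a zero count means if patients are not asked.** Let s be the chance that an event which occurs is recorded. The recorded rate is then p × s, and the two-sided limit on the true rate p becomes 0.0787/s. The documents give no value for s, so these are illustrations only:

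- s = 1: 7.9%
- s = 0.5: 0.0787/0.5 = 15.7%
- s = 0.25: 0.0787/0.25 = 31.5%
- s at or below 0.0787: 100%, so no information

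With s unknown, the zero gives no usable bound.

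**5. What complete questioning could deliver at 45 per arm.** The documents give no event rates, so those below are assumptions.

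The chance of at least one event in an arm is 1 − (1 − p)^45: 36% at p = 1%, 60% at 2%, 90% at 5% and 99% at 10%.

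Power for a difference between arms (normal approximation, two-sided 0.05) is Φ{[|p₁ − p₂| − 1.96√(2p̄(1 − p̄)/45)] / √[(p₁(1 − p₁) + p₂(1 − p₂))/45]}, where p̄ is the mean of p₁ and p₂:

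| Assumed rates | Power |
|---|---|
| 2% vs 5% | 12% |
| 5% vs 10% | 14% |
| 5% vs 15% | 35% |
| 5% vs 20% | 58% |
| 5% vs 25% | 77% |

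The checklist would therefore give descriptive rates, not a powered comparison of harm.

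**The case against.** The strongest reply is that little of the named harm separates the arms. Every patient has an IV and a running pump, so infection, thrombosis, phlebitis and redness can occur in both. Only hypervolemia is plainly tied to the volume contrast; site swelling may be, but the documents do not say so. No arm goes without an IV, so even perfect data could not estimate the harm avoided by omitting one. All of this stands, and it narrows what the checklist is for.

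The stated aim, in the Introduction, is the effect of fluids on pain, with IV risk as background. A reader might infer that, without harm data, the trial cannot weigh benefit against harm, or that a null pain result could not be acted on. The documents do not support that. They do not present this as a benefit-risk trial, and the power figures show that full questioning would not settle the matter either.

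Some harm is already captured. Admission is compared by arm, severe or unresponsive events go to the IRB, and admitted patients are seen in person. It would be too strong to say that the risks are never asked about in any patient, because the content of the inpatient contact is open.

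Two further inferences go too far. The protocol does not say that the research assistants who make the calls know the arm. Akathisia is listed for prochlorperazine, which both arms receive, so its absence from the questions is not a gap in measuring fluid harm.

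None of this supplies a rate by arm for any of the six saline risks.

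**Conclusion.** The point holds as a modest gap in safety data. The specified contacts solicit none of the six saline risks, so no rate by arm can be derived for any of them and a zero count would be uninterpretable. What is lost is mainly mild and moderate events. The primary comparison, its sample size and its validity are untouched.

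The conclusion rests on two assumptions. First, the risks in Risk/Benefit are taken to be anticipated effects under the package-insert definition, which the documents do not reproduce. Second, some site events are taken to appear after discharge. That is general clinical reasoning rather than a statement in the protocol, and some could appear after the 48-hour window as well.

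**What to change.** Add a short, fixed yes/no checklist of the named saline risks to contacts that already exist.

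- **30- and 60-minute form, and the 24-48 hour call or inpatient visit:** site swelling, redness or pain; signs of infection; signs of a vein clot or phlebitis; breathing difficulty or another sign of fluid overload.
- **Call or inpatient visit, in addition:** any return visit.
- **Method:** read from a script, by someone unaware of the arm where feasible. State the content of the inpatient contact so that it matches the call.
- **Analysis:** tabulate counts by arm, over the patients actually asked, with exact confidence intervals, as a descriptive safety outcome and whether or not the event is reportable to the IRB. State in advance that 0 of 45 would still allow a true rate of up to about 7.9%, and that the limit is higher if fewer are reached.
- **Akathisia:** leave it out, or record it only as general safety.

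The cost is a few lines on the form, about a minute more per contact, and more minor events to record. Sample size, visits and staff do not change.

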Assuming a SD of 22 (based on prior data from our institution), we calculated that we would need 45 patients in each group to find a clinically important difference in pain score reduction (13 mm) between groups at 60 min with at least 80% power and an alpha of 0.05.

The groups will be compared using a t -test on gender, race, and age; and a chi (with Yates correction)-squared test on severity of presenting headache, to determine if they are similar. The individual VAS measurements will be compared using a repeated measures analysis of variance (ANOVA) test.

REFERENCES

[1] R.B. Lipton, M.E. Bigal, M. Diamond, F. Freitag, M.L. Reed, W.F. Stewart, et al. Migraine prevalence, disease burden, and the need for preventive therapy. *Neurology*, 68 (2007), pp. 343–349

[2] B.W. Friedman, J. West, D.R. Vinson, M.T. Minen, A. Restivo, E.J. Gallagher. Current management of migraine in US emergency departments: an analysis of the National Hospital Ambulatory Medical Care Survey. *Cephalalgia*, 35 (2015), pp. 301–309

[8] Jones J, et al. Randomized double-blind trial of intravenous prochlorperazine for the treatment of acute headache. *JAMA*. 1989;261:1174-1176.

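### The 24-48 h follow-up does not record headache medicine taken after discharge, so resolution after ED treatment cannot be separated from resolution after self-treatment

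*Combined protocol and SAP*

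**What the plan says.** Under Methods of Measurement, discharged patients are telephoned one to two days after they leave. The call has two items; the callers are to "ask if they are currently having a headache (yes or no) and to rate their current pain (0-10". Admitted patients are to be approached in hospital instead; the content of that contact is not spelled out. The same section gives the one medication data source: "The need for rescue medications will be extracted from the patient's chart at a later time". The Safety section uses the term rescue medication for what the treating provider may give once 30 minutes have passed.

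Outcome Measures lists among the secondary outcomes "rate of use of additional medications for headache, and headache resolution with telephone follow up". Resolution is not defined there or under Data Analysis, and no rule covers medicine taken between discharge and the call. The primary outcome is pain, "measured as the absolute difference between the means at 60 min".

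On blinding, the Interventions section says: "The IV bag and pump will be covered so that the patient will not know how much fluid they are receiving".

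**The concern.** One to two days pass between discharge and the call. Patients whose headache persists or returns in that time are the ones likely to take something for it. Those whom it helps will answer that they have no headache, just like patients who needed nothing after the ED.

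Patients do not know their fluid volume, so home treatment should follow symptoms rather than knowledge of the arm. The arm with more remaining headache then has more patients for home medicine to convert, and the two resolution rates would be expected to move closer together.

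At stake is the interpretation of one secondary outcome. If the arms look alike at 24-48 h, the data could not show whether fluids made no lasting difference or whether home treatment narrowed a gap. Rescue in the ED can be recovered from the chart afterwards. Home use that was never asked about leaves nothing for a sensitivity analysis.

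**Working it through.** **1. The plan's own figure.** Data Analysis gives SD 22 mm, a difference of 13 mm, 80% power and alpha 0.05 (two-sided assumed; one-sided would give 36 per group). Normal approximation:

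n per group = 2 × [22 × (1.960 + 0.842) / 13]² = 2 × 4.741² ≈ 44.96, rounded up to 45.

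The stated 45 reproduces, with 80.0% power. It belongs to 60-minute pain. The documents contain no sample size, rate or power for the call.

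**2. Model for the call.** All rates below are assumptions.

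- h = proportion with headache at the call if nobody self-treated: 55% control, 40% fluid bolus.
- m = share of those patients who self-treat; e = share of self-treaters made headache-free.
- c = m × e = share converted by home medicine.

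Observed headache rate = h × (1 − c). With the same c in both arms, observed difference = (55 − 40) × (1 − c).

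Power is for a two-sided comparison of two proportions at 0.05 with 45 per arm (normal approximation, pooled variance under the null).

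| m | e | c | Control | Fluid | Difference | Power |
|---|---|---|---|---|---|---|
| none | – | 0 | 55.00% | 40.00% | 15.00 | 29% |
| 0.3 | 0.5 | 0.15 | 46.75% | 34.00% | 12.75 | 23% |
| 0.5 | 0.5 | 0.25 | 41.25% | 30.00% | 11.25 | 20% |
| 0.7 | 0.7 | 0.49 | 28.05% | 20.40% | 7.65 | 13% |

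The ratio of headache rates, fluid to control, is 40/55 = 0.73 in every row. Equal conversion shrinks the absolute difference but leaves this ratio alone.

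**3. Other assumed rates, equal c.**

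- True resolution 50% v 70% (20 points): c = 0.3 gives 65% v 79% (14 points) and c = 0.5 gives 75% v 85% (10 points). Power falls from 49% to 31% and 22%.
- True resolution 40% v 70% (30 points): 21 points at c = 0.3 and 15 at c = 0.5. Power falls from 83% to 58% and 40%.

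**4. Unequal conversion.** Starting from 55% v 40%, take c = 0.15 in control and 0.25 in the fluid arm:

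55 × 0.85 − 40 × 0.75 = 46.75 − 30.00 = 16.75 points, more than 15.

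In general the difference falls below 15 only if 55 × c(control) > 40 × c(fluid), that is, if conversion in the fluid arm is less than 55/40 = 1.375 times that in control.

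Starting from resolution of 50% v 70% (20 points):

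| c control | c fluid | Observed resolution | Difference |
|---|---|---|---|
| 0.5 | 0.3 | 75% v 79% | 4 |
| 0.3 | 0.5 | 65% v 85% | 20 |
| 0.2 | 0.4 | 60% v 82% | 22 |

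Shrinkage is the expected direction when conversion is similar, not a certainty.

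**The case against.** **The planned question is legitimate.** Headache status at 24-48 h regardless of later treatment is a sensible pragmatic outcome, and the two items measure it. The plan does not claim medication-free resolution, so dilution is a defect only if that was the target. This stands, and it is why the planned status should be kept. But the plan leaves resolution undefined, and without the extra item only one of the two readings can be reported.

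**A reader might infer that any true fluid difference must be diluted.** The documents do not support that. It needs similar conversion in both arms. Patient blinding makes similar self-treatment plausible but does not guarantee similar success, and step 4 shows the difference holding or growing when conversion differs.

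**A reader might also infer that a null result at the call would be due to home medicine.** On the assumed 55% v 40%, power with 45 per arm is only about 29% with no home medicine at all. A non-significant result would be likely either way, because the trial was sized for 60-minute pain.

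**Nor do the documents show that the additional-medication outcome stops at the ED door.** The chart is named for rescue medication, no source is stated for the separately worded additional-medication outcome, and the chart is not restricted to the ED, so inpatient medicine may be captured. The gap concerns discharged patients.

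**The extra item does not cleanly recover the undiluted contrast.** Patients who took something but would have recovered anyway would count as not resolved. That is fair, and it is the reason to treat the added endpoint as supportive.

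**Conclusion.** The point holds in a limited form. Followed as written, the plan records no headache medicine taken at home after discharge, and no analysis could recover it. Resolution at the call therefore mixes patients helped by ED treatment alone with patients helped by later self-treatment.

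Provided conversion by self-treatment is similar in the two arms, the absolute difference would be expected to shrink by the factor (1 − c). The documents allow no estimate of c or of the resolution rates, so the figures above illustrate the mechanism and do not forecast its size. The effect is confined to the 24-48 h secondary outcome; the 60-minute primary outcome and its 45 per group are untouched. This is a low-priority improvement to a call that is already planned and staffed.

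**What to change.** 1. Add one yes/no question to the phone call and to the in-hospital contact: whether the patient has taken any medicine for headache since leaving the ED.
2. Keep current headache status as planned, and state that it is reported regardless of medicine taken since.
3. Report the proportion headache-free without further medication beside it, as a supportive analysis.
4. Report post-discharge use as a separate self-reported item. Do not merge it with the chart-based additional-medication outcome: that would mix two sources and bring missing data from patients not reached into an outcome that can otherwise be read without patient contact.

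The cost is one line in the phone script and one field on the form. The drawbacks are some recall error over one to two days, missing answers from patients who cannot be reached, and a yes/no item that cannot separate a headache that persisted from one that came back.

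### The primary outcome is the 60-minute pain score, but the sample size rests on pain reduction with an SD tied to neither, so the stated 80% power cannot be attached to the defined primary

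*Combined protocol and SAP*

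**What the plan says.** Outcome Measures makes the primary outcome the difference in pain scores between the two fluid arms, "measured as the absolute difference between the means at 60 min". It mentions neither baseline subtraction nor baseline adjustment. The next sentence begins the secondary outcomes: "Secondarily, we will measure the difference between the rates of decline in pain scores".

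Data Analysis justifies the sample size on a different quantity. The effect to be detected there is a "clinically important difference in pain score reduction (13 mm) between groups at 60 min". Power is set at 80% or more and alpha at 0.05, and the stated conclusion is that "we would need 45 patients in each group". The SD is 22, attributed to the institution's own earlier data. The text does not say whether it is the SD of the 60-minute score or of the change from baseline.

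The only analysis named for the VAS is a repeated measures ANOVA on the individual measurements. No contrast is marked as primary and baseline adjustment is not mentioned. Under Methods of Measurement, a baseline VAS is taken on every enrolled patient and repeated at 30 and 60 minutes, so both the score and the reduction can be computed.

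**The concern.** A pain score at 60 minutes and a reduction in pain by 60 minutes are different variables. Randomisation gives them the same expected arm difference, so the 13 mm target carries over from one to the other. The SD, the power, the realised estimate and the p-value do not.

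Two things are at stake. First, the 80% power cannot be attached to the outcome that the plan defines, because the reader does not know which variable has the SD of 22. Second, the analysis sentence does not settle the choice: a group main effect, a group-by-time interaction and a 60-minute contrast from a repeated measures ANOVA answer different questions. That leaves room to choose after the data are seen. Simple randomisation, separate only for the adult and pediatric EDs, does nothing to balance baseline pain, and baseline imbalance is exactly what separates the two estimates.

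**Working it through.** **Inputs from Data Analysis:** difference 13 mm, SD 22, 45 per arm, 80% power, alpha 0.05.

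**Assumptions, not in the documents:** a two-sided test (it reproduces the plan's figure; one-sided gives 36 per arm); normality; a baseline-to-60-minute correlation r of 0.3, 0.5 or 0.7; and equal SDs at the two times unless stated.

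**1. The plan's own figure.** n = 2 × [22 × (1.9600 + 0.8416) / 13]² = 44.96, so 45 per arm. Power at 45 is 80.0% by the normal approximation and 79.2% by the t distribution. The arithmetic is sound.

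**2. How far apart the two estimates can be.** The arm difference in reduction equals, apart from sign, the arm difference in 60-minute score minus the arm difference in baseline. With a baseline SD of 22, the latter has standard error 22 × √(2/45) = 4.64 mm, and 1.96 × 4.64 = 9.1 mm, which is 70% of the 13 mm target. With a baseline SD of 15 the standard error is 15 × √(2/45) = 3.2 mm.

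**3. What the SD of 22 implies for the other variable.** With equal SDs, SD of reduction = SD of score × √(2(1−r)). Power is from the noncentral t, 45 per arm, difference 13 mm.

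| r | If 22 is the score SD: SD of reduction | Power for reduction | If 22 is the SD of the reduction: SD of score | Power for score |
|---|---|---|---|---|
| 0.3 | 26.0 | 65% | 18.6 | 91% |
| 0.5 | 22.0 | 79% | 22.0 | 79% |
| 0.7 | 17.0 | 95% | 28.4 | 57% |

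The two readings coincide only at r = 0.5, and only because the SDs at the two times were assumed equal.

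**4. How often the two tests disagree.** 40,000 simulated trials per setting, 45 per arm, SD 22 at both times, one t-test on the score and one on the reduction, each at 0.05.

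| r | Disagree, true 13 mm effect | Disagree, no effect | Type I error if either may be chosen |
|---|---|---|---|
| 0.3 | 27% | 7.5% | 8.7% |
| 0.5 | 24% | 8.1% | 9.0% |
| 0.7 | 21% | 8.8% | 9.5% |

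With a baseline SD of 15 and a 60-minute SD of 22, disagreement at a true 13 mm effect falls to about 16% to 19%.

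**5. The baseline-adjusted comparison.** With baseline VAS as covariate, subtracting baseline from the response changes only the baseline coefficient. The treatment estimate and p-value are therefore identical for score and reduction. The residual SD is score SD × √(1−r²).

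| r | If 22 is the score SD: residual SD | Power | If 22 is the SD of the reduction: residual SD | Power |
|---|---|---|---|---|
| 0.3 | 21.0 | 83% | 18.59 × √(1−0.09) = 17.7 | 93% |
| 0.5 | 19.1 | 89% | 22.00 × √(1−0.25) = 19.1 | 89% |
| 0.7 | 15.7 | 97% | 28.40 × √(1−0.49) = 20.3 | 85% |

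**The case against.** The strongest reply is that only Outcome Measures declares a primary outcome, and it does so clearly: mean scores at 60 minutes. The word reduction appears in a sample size rationale and may be loose wording for the same contrast, since the expected difference is the same. Listing rates of decline as secondary supports this, because it suggests that change was meant to stand apart from the primary. All of that is fair. A reader might infer that the plan declares two rival primary outcomes; the documents do not go that far. What remains is that the plan nowhere says reduction means score, nor which of them the 22 measures.

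A reader might also infer that 22 is the SD of the reduction, because it stands in the same sentence, or that the trial is underpowered. Neither is supported. The text ties the SD to no variable, the 45 per arm reproduces, and power for the other variable may be higher or lower than 80% depending on r.

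The disagreement rates compare two t-tests, whereas the plan names an ANOVA for the VAS, and they depend on assumed SDs and correlations. This is so, and the rates are illustrations rather than predictions. It does not rescue the plan, because an ANOVA without a stated contrast leaves the same choice open.

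Finally, choosing either existing variable and aligning the sections would remove the inconsistency without ANCOVA. That is correct; ANCOVA is preferred because it also makes the choice between score and reduction immaterial and uses a baseline that is already collected.

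**Conclusion.** The point stands as a mismatch between the defined primary variable, the variable used for sizing and an analysis with no primary contrast. The wording mismatch is certain; its numerical consequences are conditional. With SDs of 22 at both times and r from 0.3 to 0.7, score and reduction give different verdicts at p<0.05 in about 27% to 21% of trials with a true 13 mm effect (about 16% to 19% if the baseline SD is 15). Free choice between them takes type I error from 5% to about 9%. Over the same r, power for whichever variable does not own the SD of 22 runs from 65% to 95% if that variable is the reduction, and from 91% down to 57% if it is the score. The sample size arithmetic is not at fault, and the true effect being estimated is the same either way. This should be settled before any unblinded comparison.

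**What to change.** 1. In Outcome Measures and in Data Analysis, state one primary analysis: the between-arm difference in 60-minute VAS, adjusted for baseline VAS by ANCOVA. The unadjusted score and the raw reduction can be reported descriptively.
2. Amend the repeated measures ANOVA sentence so that it covers only the secondary comparison over time. If it is left as it is, endpoint and analysis will still disagree.
3. Check the institutional data and state whether 22 is the SD of the 60-minute score or of the reduction. Do not label it the adjusted SD: if 22 is the score SD, the adjusted value is 21.0, 19.1 or 15.7 at r = 0.3, 0.5 or 0.7.

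The 45 per arm can stay. At these correlations adjusted power is 83% to 97% if 22 is the score SD and 85% to 93% if it is the SD of the reduction. The cost is a few sentences across two sections and a look at the source of the SD, with no new measurements or patients.
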